2. LIST OF ABBREVIATIONS

AE	Adverse Event
CACG	Chronic Angle-Closure Glaucoma
CFR	Code of Federal Regulations
CRO	Contract Research Organization
eCRF	electronic Case Report Forms
EFSA	European Food Safety Authority
FDA	Food and Drug Administration
GCP	Good Clinical Practice
ICH	International Conference on Harmonization
ICMJE	International Committee of Medical Journal Editors
IEC	Independent Ethics Committee
IOP	Intraocular Pressure
IRB	Institutional Review Board
LOCS	Lens Opacities Classification System
MP	Monitoring Plan
MD	Mean Deviation
MedDRA	Medical Dictionary for Regulatory Activities
NTG	Normal Tension Glaucoma
OCT	Optical Coherence Tomography
ONH	Optic Nerve Head
PEX	Pseudoexfoliation
PT	Preferred Term
SAE	Serious Adverse Event
SF-36	Short Form Health Survey – 36 items
SITA	Swedish Interactive Threshold Algorithm
SOC	System Organ Class
SUSAR	Suspected Unexpected Serious Adverse Reaction
VA	Visual Acuity
VF	Visual Field
VFQ	Visual Functioning Questionnaire – 25 items

Clinical Trial Protocol NEUQOL2018

OPKO Health

WHO-DD World Health Organization Drug Dictionary

3. PROTOCOL SUMMARY

Background: Primary open angle glaucoma is a chronic progressive neurodegenerative disease and the only proven effective therapy involves reduction of intraocular pressure (IOP). Although treatment effect is quite large, a significant proportion of patients show disease progression with apparently controlled IOP.¹ Given the similarities with other neurodegenerative diseases – particularly in the mechanisms of cell death – neuroprotective treatments have been tried also in glaucoma. Interesting results from experimental studies and weak evidence from human glaucoma trials have been published in recent years. Citicoline is one of the promising molecules with a putative neuroprotective action and has been tried on patients with a number of neurodegenerative diseases with encouraging results.² Pilot studies on glaucomatous patients showed a possible effect of citicoline in reducing progression of visual field changes,³ though these findings need to be confirmed by larger randomized clinical trials. One of the different explanations for the effect of citicoline on visual field changes is related to its dopaminergic action, which also has positive repercussions on psychophysical performances.

Aims: The main objective of the study is to test whether the intake of Neurotidine[®] (citicoline free acid in oral solution) can be associated with an improvement of quality of life in patients with glaucoma. Other objectives are the assessment of the tolerability and safety of Neurotidine[®].

Design: This is a randomized, double-masked, placebo-controlled, cross-over study. After informed consent and verification of eligibility, patients will be randomized in a 1:1 ratio to a Neurotidine[®]-placebo or placebo-Neurotidine[®] sequence and receive treatment for 3 months

in the first period and for six months in the second period of the cross-over design. The second period will be extended to 6 months in order to control for potential carry over effect in the group receiving Neurotidine[®] in the first period of the cross-over design.

Treatment: Neurotidine[®] or placebo will be administered at a dosage of 10 ml in the morning.

- Neurotidine[®]: 500 ml oral solution containing citicoline free acid 50 mg/ml.
- Placebo: 500 ml oral solution indistinguishable from active product in appearance and taste.

Patients: A total of 200 patients will be evaluated in this study, ideally 40 per center, with a minimum of 20 and a maximum of 50 per centre, though enrollment will be competitive.

- Inclusion criteria:
 - Signed written informed consent.
 - Age \geq 18 years.
 - Patients with bilateral open-angle glaucoma (OAG). PEX and pigmentary glaucoma will be included.
 - Controlled IOP
 - Patients with moderate damage in the better eye, with mean deviation from normal value (MD) ranging from -6 to -12 dB in the 6 months prior to enrollment. At the screening assessment, MD must range from -5 to -13 dB.

Glaucoma definition will be based on visual field (VF) damage (24-2, SITA standard strategy) corresponding to glaucomatous changes at the optic nerve head. Values of IOP will not be an inclusion criterion, though a “controlled IOP” based on the clinician’s judgement will be required.

- Exclusion criteria
 - Single-eyed patients (visual acuity <0.1 in one eye).

-
- Patients without the psychophysical requirements to adequately participate and complete the trial.
 - Patients with chronic angle-closure glaucoma (CACG) or other types of glaucoma.
 - Patients with other ocular comorbidities interfering with the correct assessment of the glaucomatous damage to the VF.
 - Patients who have undergone surgery within 6 months.
 - Patients taking other potential neuroprotectors, including topical, competing with Neurotidine[®].
 - Patients with Parkinson's disease, dementia or a diagnosis of stroke in the last 6 months.

Study outcomes: The primary outcome will be the mean change of “intra-patient” global score of the VFQ-25 questionnaire after Neurotidine[®] vs placebo at 6 months as compared to baseline. Other outcomes include the change of other scores (e.g. general health, general vision, near and far activities, social, mental, role difficulties, etc.) of two study questionnaires, VFQ-25 and SF-36, as well as the safety and tolerability of citicoline oral solution.

4. SCHEDULE OF ASSESSMENTS

	Screening / Baseline (beginning of 1 st period)	3-month Visit (end of 1 st period, beginning of 2 nd period)	6-month Visit	9-month Visit (end of 2 nd period)
Informed consent	X			
Inclusion/exclusion criteria	X			
Complete ophthalmological examination*	X	X	X	X
Randomization to study sequence	X			
VFQ-25	X	X	X	X
SF-36	X	X	X	X
Dispensing treatment	X	X	X	
Concomitant medications	X	X	X	X
Adverse events		X	X	X

*Including visual acuity (VA), VF (24-2, SITA standard strategy), fundus assessment, biomicroscopy (with specific lens evaluation using Lens Opacities Classification System III (LOCS III) criteria), IOP assessment. Gonioscopy and optic nerve head (ONH) topography parameters measured by optical coherence tomography (OCT) are required at screening to verify inclusion/exclusion criteria.

5. INTRODUCTION

Glaucoma is a chronic and progressive neurodegenerative disease with unknown etiology. A number of factors are involved in the pathogenesis, though increased IOP remains the most important. However, elevated IOP cannot explain disease progression in many cases: data

from large clinical trials are consistently showing a variable (and relevant) proportion of glaucoma patients experiencing worsening of visual field despite apparent IOP control.¹ It is thus very likely that mechanisms other than IOP are involved in the pathogenesis of the disease.

A bulk of experimental data has shown similarities in the mechanisms of cell death across different neurodegenerative diseases. Glaucomatous optic neuropathy shares the way cells die and mechanisms of trans-synaptic neurodegeneration with neurologic diseases such as Parkinson's disease, Alzheimer's disease, amyotrophic lateral sclerosis etc.^{4,5} There is growing evidence that glaucomatous damage involves all the visual pathways from the retina back to the lateral geniculate nucleus and the visual cortex. Today we can say that glaucoma can be considered a brain disease. As the main and starting event in glaucoma is the death of the retinal ganglion cell, neuroprotective strategies have been postulated. All possible molecules with a putative effect on glaucomatous neurodegeneration have been tested in vitro, in vivo in animal models, but only a few in human glaucoma. Today, there are about a dozen clinical trials in glaucoma showing products with a possible neuroprotective effect. The main problem is that most of these studies are grossly undersized to clearly demonstrate an effect on glaucoma progression.

There have been 2 large trials on neuroprotection in glaucoma, both with surprising outcomes. One tested memantine on about 2,000 patients with high-risk of progressive glaucoma: despite the large sample size the trial failed to reach the primary end-point (required by FDA). There is substantial lack of information about the details of what happened in this study as findings were never published. The other study tested brimonidine on low-tension glaucoma patients and the drug was found unexpectedly to be "extremely" effective in reducing disease

progression.⁶ However, some methodological flaws of the trial casted doubts on the validity of the findings and, as a matter of fact, brimonidine did not become the first-choice therapy for normal tension glaucoma (NTG) patients despite the evidence of a significant effect.

The action of citicoline in patients with neurodegenerative disorders has been known for a long time and today there are hundreds of publications about the efficacy of the molecule in patients with dementia, stroke, Parkinson's disease and glaucoma.² There is a systematic review from the Cochrane database reporting that citicoline can be effective in improving activity scores in patients with some stage of senile dementia.⁷ The mechanisms of action include “cell protection” (as it is part of the cell membrane), reduction of cell apoptosis and a positive effect on the synthesis of neurotransmitters – both dopaminergic and cholinergic.

Citicoline can be administered systemically (intramuscular, oral) and topically. Most of the literature on the effect of citicoline is based on systemic intramuscular administration.⁸ Since some years ago, similar bioavailability can be obtained with oral solution, a more practical and comfortable way of administration for chronic diseases where citicoline needs to be given daily for years.^{9,10} There is evidence that citicoline oral solution has 98% bioavailability.⁹ Recently, citicoline free acid has been authorized in Europe by the EFSA (European Food Safety Authority) as a Novel Food ingredient also for Special Medical Purpose, and according to this new classification, a form in oral solution (Neurotidine[®]) has been registered as Food for Special Medical Purpose with therapeutic Indication: “Glaucomatous patients with stable IOP, but with a progressive loss of Visual Field (VF)”. Citicoline eyedrops are also available in many European Countries.

6. OBJECTIVES

Today there is growing evidence (though still weak) that citicoline can be an effective complementary treatment for glaucoma patients. Awaiting large clinical trials to confirm the effectiveness of citicoline in reducing the progression of glaucoma, the rationale for this study includes the assessment of the role of the molecule on the dopaminergic pathway and particularly its potential implications on psychophysical performance and quality of life. Other objectives are the assessment of the tolerability and safety of Neurotidine[®] (citicoline oral solution).

7. STUDY OUTCOMES

The primary outcome will be the mean change of “intra-patient” global score of the VFQ-25 questionnaire after Neurotidine[®] vs placebo at 6 months compared to baseline. Other outcomes include the change of other scores (e.g. general health, general vision, near and far activities, social, mental, role difficulties, etc.) of two study questionnaires, VFQ-25 and SF-36, as well as the safety and tolerability of citicoline oral solution.

8. PATIENTS

A total of 200 patients will be evaluated in this study, ideally 40 per center, with a minimum of 20 and a maximum of 50 per centre, though enrollment will be competitive. Inclusion and exclusion criteria will be ascertained through a complete ophthalmic examination including VF test, gonioscopy and optic nerve head (ONH) topography parameters measured by optical coherence tomography (OCT).

8.1 Inclusion Criteria

Patients must meet all the following criteria to be eligible for the study:

-
- Signed written informed consent.
 - Age \geq 18 years.
 - Patients with bilateral open-angle glaucoma (OAG). PEX and pigmentary glaucoma will be included.
 - Controlled IOP
 - Patients with moderate damage in the better eye, with mean deviation from normal value (MD) ranging from -6 to -12 dB in the 6 months prior to enrollment. At the screening assessment, MD must range from -5 to -13 dB.

Glaucoma definition will be based on visual field (VF) damage (24-2, SITA standard strategy) corresponding to glaucomatous changes at the optic nerve head. Values of IOP will not be an inclusion criterion, though a “controlled IOP” based on the clinician’s judgement will be required.

8.2 Exclusion Criteria

Patients must meet none of the following criteria to be eligible for the study:

- Single-eyed patients (visual acuity <0.1 in one eye).
- Patients without the psychophysical requirements to adequately participate and complete the trial.
- Patients with chronic angle-closure glaucoma (CACG) or other types of glaucoma.
- Patients with other ocular comorbidities interfering with the correct assessment of the glaucomatous damage to the VF.
- Patients who have undergone surgery within 6 months.
- Patients taking other potential neuroprotectors, including topical, competing with Neurotidine[®].
- Patients with Parkinson’s disease, dementia or a diagnosis of stroke in the last 6 months.

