9. TREATMENTS

Patients will be treated with any IOP-lowering agent to control the disease. The type and number of drugs will be decided by the treating clinician. Previous laser and/or surgery will be allowed but not within 6 months prior to study enrollment.

After signing of the informed consent form and ascertainment of eligibility, patients will be randomized in a 1:1 ratio to a Neurotidine[®]-placebo or placebo-Neurotidine[®] sequence and receive treatment for 3 months in the first period and for six months in the second period of the cross-over design. The second period will be extended to 6 months in order to control for potential carry over effect in the group receiving Neurotidine[®] in the first period of the cross-over design.

Neurotidine[®] 500 ml oral solution contains citicoline free acid 50 mg/ml; water; fructose; acidity regulators: sodium citrate, sodium hydroxide; preservative: potassium sorbate; color: riboflavin.

Placebo 500 ml oral solution contains water, fructose, sucralose; acidity regulators: sodium citrate, anhydrous citric acid, sodium hydroxide; preservative: potassium sorbate; color: riboflavin.

In addition to the IOP-lowering medications, Neurotidine[®] or placebo will be administered at a dosage of 10 ml in the morning.

Bottles of Neurotidine[®] and placebo oral solutions will be identical (same ingredients except for citicoline), containing 500 ml of a yellow solution with a measuring cup. Neurotidine[®] and placebo solutions will have similar taste. Each patient will be given the bottles for the first 3-month treatment period by the hospital pharmacist and will be asked to return them at the end

of the period (3 months). Then the patients will be given the other bottles for the next phase of the study (3 months): these will contain placebo if the patient received Neurotidine[®] in the first phase of the study and vice versa. Again, the patients will be asked to return after 3 months with the study bottles and will be given the last set of bottles for the final phase of the study (3 months): in this phase the bottle contents will be the same as in phase 2.

Information about compliance with treatment will be recorded at each visit. All study bottles will be collected and sent to the coordinating center.

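### The neuroprotector exclusion has no look-back and no run-in precedes period 1, so patients who have just stopped citicoline can enter and may dilute the first placebo period

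*Combined protocol and SAP*

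**What the plan says.** The only eligibility rule on neuroprotectors is in Section 8.2, repeated in the Protocol Summary (Section 3). It excludes "Patients taking other potential neuroprotectors, including topical, competing with Neurotidine". No time window is attached. Two neighbouring criteria in the same list do have one: "Patients who have undergone surgery within 6 months" and "a diagnosis of stroke in the last 6 months".

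The Introduction (Section 5) shows that citicoline is already on the market for this kind of patient. It says that Neurotidine "has been registered as Food for Special Medical Purpose with therapeutic Indication" in glaucoma, and that "Citicoline eyedrops are also available in many European Countries".

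The Schedule of Assessments (Section 4) has one entry visit, in a column whose heading begins "Screening / Baseline (beginning of 1". Consent, eligibility, randomisation, the baseline questionnaires and the first dispensing all fall there. There is no run-in or washout.

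Section 9 recognises carry-over within the trial: "The second period will be extended to 6 months in order to control for potential carry over effect". The sentence goes on to limit this to the group given Neurotidine first.

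Prior medications are coded (Section 12.1.2) and tabulated by treatment group (Section 14). Randomisation is stratified by centre only (Section 10), and the primary ANOVA has terms for sequence, subject, period and treatment (Section 14). None of these uses prior citicoline.

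**The concern.** A patient who stopped citicoline the day before screening meets no exclusion. Such a patient can be randomised and complete the baseline VFQ-25 at that visit, then start period 1. If allocated to placebo first, the patient has the only period 1 assessment three months after the last citicoline. By extending the second period beyond three months, the protocol signals that three months on placebo may not be enough for trial citicoline to clear. Nothing comparable applies at entry.

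Two things are at stake. First, any effect still present at month 3 raises the placebo score in the placebo-first sequence and narrows the Neurotidine-minus-placebo contrast. Second, the objective is improvement and the primary outcome is expressed against baseline. In a recent user, the baseline may already include some citicoline effect, so change from it is harder to read as improvement.

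There is also a wording problem. Because the rule speaks of *other* products competing with Neurotidine, it does not clearly say that a patient now taking Neurotidine is excluded.

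**Working it through.** **Inputs from Section 13.** Difference 3.0; root MSE 10.607; SD of differences 15.0; 100 patients per sequence (N = 200); two-sided alpha 0.05; power 80%.

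**Step 1: reproduce the stated power.**
- SD check: 10.607 × √2 = 15.0.
- Standard error of the treatment difference: 10.607 × √(2/200) = 1.061.
- Non-centrality: 3.0 / 1.061 = 2.83, with 200 − 2 = 198 degrees of freedom.
- Power by the noncentral t distribution: 80.4%. The stated 80% is reproduced, and this point disputes no figure in Section 13.

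**Step 2: effect of recent users on the expected difference.** Let p be the share of enrolled patients who recently stopped citicoline, equal in expectation in both sequences because of 1:1 randomisation. Let r be the fraction of the 3.0-point effect still present at month 3 on placebo. Assume that trial Neurotidine gives recent users the same full effect as other patients and no more, that the period 2 placebo score is clean, and that the variance is unchanged.
- Neurotidine-first sequence: expected contrast 3.0.
- Placebo-first sequence: the placebo mean is raised by 3.0 × p × r, so the contrast is 3.0 × (1 − p·r).
- Average over two equal sequences: 3.0 × (1 − p·r/2).

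**Step 3: put in a range.** The documents give neither p nor r, so the values below are assumptions. The N for equal power is 200 × (3.0 / expected difference)², rounded up.

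| p | r | Expected difference | Power at N = 200 | N for equal power |
|---|---|---|---|---|
| 0 | – | 3.00 | 80.4% | 200 |
| 10% | 0.5 | 2.925 | 78.4% | 211 |
| 10% | 1 | 2.85 | 76.2% | 222 |
| 20% | 0.5 | 2.85 | 76.2% | 222 |
| 20% | 1 | 2.70 | 71.7% | 247 |
| 30% | 0.5 | 2.775 | 74.0% | 234 |
| 30% | 1 | 2.55 | 66.7% | 277 |

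Worked example: p = 30%, r = 1 gives 3.0 × (1 − 0.30/2) = 2.55; 2.55 / 1.061 = 2.40; power 66.7%.

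**Step 4: direction.** If one baseline serves both periods, the within-patient contrast is (Neurotidine − baseline) − (placebo − baseline) = Neurotidine − placebo. A raised baseline cancels. What remains is the raised month-3 placebo score, which moves the estimate toward zero.

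**The case against.** Several points on the other side are sound.

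- A reader might infer that current users of any marketed citicoline can enter. The text does not support that. A rule on other neuroprotectors that expressly includes topical ones naturally covers citicoline eyedrops and other brands. Only Neurotidine itself is left in doubt, and only on a literal reading of *other*.
- A reader might go further and suppose that patients will continue their own supply throughout the trial. Nothing in the documents indicates this, and concomitant medications are recorded at every visit. No figure is attached to that scenario here.
- Carry-over into period 1 is conditional. Section 9 calls carry-over potential and ties it to trial Neurotidine, which every patient in that sequence is assigned. Pre-trial use would affect an unknown subset, spread over both sequences. The Introduction shows that products exist, not how many enrolled patients used them.
- The size and the remedy pull against each other. If half or more of the effect lasts three months, a three-month look-back would leave the baseline affected. If little lasts that long, the month-3 placebo score is already nearly clean and the power loss is small.
- Prior medications are collected, so an analysis by prior use may need little new data. The documents do not say whether stop dates are recorded.

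These points limit the size of the concern and leave the length of the look-back to the sponsor. They do not close the gap: no look-back, no run-in, and no use of prior citicoline in stratification, the model or a planned sensitivity analysis.

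**Conclusion.** The concern holds in a limited form. As written, a patient who has just stopped citicoline is eligible, the exclusion of current Neurotidine use is unclear, and the longer second period cannot protect a first placebo period. If some effect persists, the expected result is dilution toward no difference. For 10% to 30% recent users and half to full persistence at month 3, power falls from 80.4% to between 78.4% and 66.7%. At the mild end the loss is about two percentage points. All of this rests on assumed p and r and on the simple model above.

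A reader might infer that the gap biases the trial in favour of Neurotidine. The documents do not support that, because a common baseline cancels from the within-patient contrast. Interpretation is a separate matter: where an earlier effect fades on placebo, part of a treatment difference would reflect loss after withdrawal, and the planned analysis cannot separate this from gain. The gap is worth closing because a design with 80% power has little to spare and the correction is cheap.

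**What to change.** 1. Reword the criterion in Section 8.2 and in the Protocol Summary so that it covers current and recent use of any citicoline product, Neurotidine included, or another neuroprotector.
2. State a look-back. The sponsor should set and justify its length in line with its own carry-over assumption. The three months added to period 2 are one reference point; the documents give no duration of effect that would settle it.
3. Record at screening the date of last use of any such product.
4. Add a sensitivity analysis that repeats the primary analysis without recent users, with *recent* defined before unmasking. This matters most for anyone enrolled before the change or in breach of it.

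Cost: one eligibility sentence in two places, one eCRF date field and one extra analysis. The planned sample size does not change. Some recent users would be excluded or enrolled later, so recruitment may be slightly slower.
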